Protocol Number: 18-DA-N095

Title: **Just-In-Time Adaptive Interventions for Addictive Behaviors (JITAI)**

Date of this submission: December 18, 2019 / Version 2.2

NIH Principal Investigator:

[name].
Branch: CPTR
Institute: NIDA IRP
[name]
[name]
[name]
[contact]
email: [contact]

A. Précis

Background. Our research group has made extensive use of ecological momentary assessment (EMA) to understand people's daily experiences with opioid craving, use, and lapse. We have also administered clinic-based psychotherapies such as cognitive-behavioral therapy (CBT), in which clients learn to avoid, escape, resolve, or reframe problems (such as stress) that can trigger lapses to drug use. CBT contrasts with ACT (Acceptance and Commitment Therapy), a mindfulness-based approach in which difficult thoughts and feelings are viewed as necessary and potentially valuable components of a full life, to be experienced observantly rather than resolved or reframed. CBT and ACT can and do coexist in a single treatment plan, but we know of no systematic attempt to reconcile their differences. We have also not tried to administer either of them on a mobile device.

Objective. To test a just-in-time adaptive intervention (JITAI)—a treatment given when and where it is needed. Our JITAI will be delivered via smartphone app and will combine elements of two widely used treatments for addiction: CBT and ACT. Our goal is *not* to bring another branded app onto the market, but rather to clarify when and for whom the generic components of such apps are effective or not. This will include determining when CBT is more helpful than ACT and vice versa.

Participant population. Outpatient adults who are in treatment for opioid use disorder (OUD)—up to 185 enrolled (35 for a formative-interview phase, 150 for a trial) for a target of 115 evaluable (30 interviewees, 85 trial participants). Target enrollment will include 40% women and 60% minorities (mostly African-American). In the trial, some participants will receive buprenorphine in our clinic, and others will be receiving buprenorphine or methadone elsewhere; this is a procedural matter, not a component of the experimental design.

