Primary outcome measures: (1) Proximal effects of CBT and ACT messages in the JITAI group: decreases over 20-minute intervals in craving and negative mood, with increases in self-efficacy; (2) strategy-situation fit in the JITAI group; (3) group differences in distal effects of treatment (week 11 versus week 2) in terms of self-efficacy and coping flexibility.

Secondary outcome measures: (1) Trait predictors of differential responses to CBT and ACT, in the JITAI group; (2) group differences in frequency of opioid-positive urine over time; (3) time courses of responsiveness to ACT vs. CBT, in the JITAI group; (4) whether the intervention types that benefit participants most when “pushed” by the app are the same ones participants choose when subsequently given the opportunity to “pull” interventions.

B. Table of Contents

A. Précis.....	2
B. Table of Contents.....	4
C. Background.....	5
1. From mobile assessment to mobile treatment: a microrandomization approach	5
2. Momentary interventions to be tested in the first arm of this protocol.....	7
3. Two ways to deliver a momentary intervention: push versus pull.....	9
4. Rationale for a multiple-arm protocol.....	10
D. Study objectives	10
E. Study design and methods	11
1. Overview of arm 1.....	11
2. Arm 1, Phase 1: Formative interviews.....	12
3. Arm 1, Phase 2: Clinical trial with microrandomization.....	12
F. Inclusion and exclusion criteria	24
1. Inclusion criteria.....	24
2. Exclusion criteria.....	24
G. Clinical and laboratory methods	25
H. Collection and storage of human specimens or data.....	30
I. Statistical analysis.....	31
1. Outcome measures.....	31
2. Analysis of study outcomes	31
3. Criteria for statistical significance.....	34
J. Required sample size	35
K. Plans for enrollment at multiple sites.....	36
L. Human-subjects protection plan	36
1. Rationale for subject selection based on gender/ethnic/race categories at risk.....	37
2. Recruitment plan	37
3. Justification for exclusion of vulnerable populations	38
4. Evaluation of risks/discomforts and benefits ratio	39
5. Subject monitoring	43
6. Conflicts of interest.....	44
M. Protection of participants' privacy and confidentiality	45
N. Study agents/interventions.....	45
O. Plan for reporting unanticipated problems and adverse events.....	45
P. Data and safety monitoring	45
Q. Clinical monitoring plan.....	46
R. Data/records management	46
1. Quality assurance.....	46
2. Relationship to other protocols	47
3. Data-sharing description.....	47

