In the second part of the interview, we will show the the interviewee our plans (below) for a treatment app, using item lists, onscreen mockups, and/or functional demos. For all that material, we will ask interviewees to comment on its likely usefulness, its likely pitfalls or possible barriers to using it, and how we could improve it. We will also compile a wish list of app features and a list of things we should avoid.

Interviews will be audiotaped, and the tapes will be transcribed by a HIPAA-compliant service.

We have prior experience conducting this type of qualitative research with our participant population (Heinz et al., 2010).

3. Arm 1, Phase 2: Clinical trial with microrandomization

The following table shows the general timeline, which is explained in the sections that follow. *For analytical purposes, there are only two groups (JITAI vs. EMA control).* Procedurally, some participants will receive buprenorphine here at Archway (OBOT participants) and others will be treated elsewhere (TE participants). The recruitment of both OBOT and TE participants is not intended to bear directly on the science of the protocol; rather, it helps us enroll participants more quickly (our experience in the 020 protocol is that we enroll

an average of 4 OBOT participants and 4 TE participants every 30 days) and, as an additional advantage, may expand the population to which we can generalize our results (though we have not seen any appreciable demographic differences between OBOT and TE participants).

week	JITAI (OBOT)	EMA control (OBOT)	JITAI (TE: Treatment Elsewhere)	EMA control (TE: Treatment Elsewhere)
1	stabilize on bup; intro session (EMA + CBT/ACT); baseline questionnaires	stabilize on bup; intro session (EMA); baseline questionnaires	intro session (EMA + CBT/ACT); baseline questionnaires	intro session (EMA); baseline questionnaires
2				
3				
4				
5	JITAI – push 4x/day (first 16 nights will also include “Deep Dive” lessons/exercises on smartphone)			
6		EMA	JITAI – push 4x/day (first 16 nights will also include “Deep Dive” lessons/exercises on smartphone)	EMA
7				
8				
9				
10	JITAI – pull		JITAI - pull	
11	outcome assessment	outcome assessment	outcome assessment	outcome assessment
12				
13				
14	bup taper or transfer	bup taper or transfer		
15				
16				

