Participants in the formative-interview phase may reenroll for the randomized treatment phase. We want to give them access to the potential benefits of the intervention. When we analyze results, we will test whether the interviewed participants respond differently from newly enrolled participants, as might be expected from their having had input into the app design.

After signing informed consent, each participant will be randomly assigned to one of two groups: JITAI intervention or EMA only.

During the first two weeks of participation, each participant will have an in-person session for training appropriate to his or her study group. All participants will be shown how to use the smartphone to make entries. Participants randomized to the JITAI intervention will be introduced to some basic principles of CBT and ACT. We are forgoing extensive in-person training in the hope of demonstrating that our ambulatory intervention can be effective without that. Mindfulness and ACT, like CBT, can be learned through “unguided self-help” (that is, without in-person training) (Cavanagh et al., 2014). A mere 11 minutes of prerecorded audio instruction on mindfulness, delivered in a clinic, was superior to a relaxation control condition

in helping at-risk drinkers reduce their drinking over the next week (Kamboj et al., 2017). We will provide more support: during the initial in-person session, each participant will watch a video introduction to both CBT and ACT. The video will be approximately 20 minutes long, and will be recorded by a counselor who has experience delivering these kinds of interventions for addiction. We will use just one counselor to discuss both techniques to avoid any confounding by participant preference for one counselor over another.

Before and after the video, one of the investigators at our clinic will talk with the participant to address concerns and discuss any material that the participant found unclear. Investigators will also be available to answer participants' questions about CBT and ACT throughout their time in the study, either during clinic visits, or by phone or online.

The content of the video will be underscored and complemented by a series of lessons/exercises that participants will read at home on their smartphone, one per night, for the first 16 nights of the JITAI intervention. We describe the lessons/exercises (to be referred to as "Deep Dives") further down, after we describe the JITAI intervention.

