2. Analysis of study outcomes

Hypothesis 1, proximal: Main effect of messaging (delivery of either a CBT-based or ACT-based message will increase self-efficacy and decrease cravings and other negative states 20 minutes later, compared with the control message).

We will use multilevel random-intercept models (with data from the JITAI group only) to test the hypothesis of a proximal benefit of messages. The dependent variables, in separate models, will be participants' ratings of self-efficacy, craving, mood, and message helpfulness in EMA "post" assessments, controlling for the ratings in "pre" assessments. The main independent variable will be message type: active (CBT or ACT) versus none ("thank you" control condition). We will use an autoregressive error structure to account for within-person correlations. A significant beneficial effect on any of the outcome measures (self-efficacy, craving, mood, message helpfulness) will be taken as partial support for the hypothesis; significant beneficial effects on all the outcome measures will be taken as full support.

Hypothesis 2, proximal: Strategy-situation fit (the effects of the messages will be moderated by the circumstances in which they are provided).

The main analysis here (again, with data from the JITAI group only) will be a test of whether CBT messages are most effective in controllable situations and ACT messages are most effective in noncontrollable situations. We will categorize a situation as *noncontrollable* when a participant gives a response of less than 50/100 on either of these two "pre" items: (1) "I could easily be somewhere else right now if I wanted," (2) "I could easily get out of what I'm doing right now." Otherwise, we will categorize the situation as *controllable*. In the subset of instances in which an active message was given, multilevel models similar to those for hypothesis 1 will be run with the predictors Intervention Type (either CBT or ACT), controllability (y/n), and their interaction. A significant interaction (in the expected direction) on any of the outcome measures (self-efficacy, craving, mood, message helpfulness) will be taken as partial support for the hypothesis; significant beneficial effects on all the outcome measures will be taken as full support.

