For each participant in the JITAI group, we will use multilevel models with person-specific slopes to quantify the relative overall effectiveness of CBT vs. ACT messages during the “push” weeks, in terms of proximal changes craving, self-efficacy, and/or mood. We will then calculate the participant’s relative overall preference for CBT vs. ACT content during the “pull” week. These can be straightforwardly shown in a scatterplot with an accompanying bivariate correlation coefficient.

3. Criteria for statistical significance

The criterion for statistical significance will be set at $p \leq 0.05$, two-tailed. For hypothesized effects that do not reach statistical significance, we will calculate Bayes factors (Dienes, 2014), which help determine whether “nonsignificant” findings favor the null or the alternative hypothesis or whether they should be considered inconclusive.

J. Required sample size

For the formative-interview phase, we anticipate that 30 interviewees will be sufficient to give us feedback on our prototype materials and app interface. We may revisit this if we find that responses are highly variable across interviewees. We expect that most people who agree to be interviewed will provide usable information, so we are setting out enrollment ceiling at 35.

For the microrandomized trial, which is longer and more demanding, we expect a higher rate of dropout. We will enroll up to 150 participants to reach a target of 85 (50 JITAI, 35 EMA control) who complete the week-eleven outcome assessment. The calculations that led us to that total are as follows.

For hypothesis 1 (the proximal main effect of messaging in the microrandomized trial), we used a power-and-sample-size calculator <<https://pengliao.shinyapps.io/mrt-calculator/>> developed specifically for microrandomized studies (Liao et al., 2016). This calculation applies specifically to the JITAI group, not the EMA control group. As Liao et al. (2016) point out, there is very little precedent for determining what a proximal effect size should look like, but small studies with microrandomized designs can often detect seemingly small effects, on the order of $d = .15$. We decided that the most important consideration was to set our beta level high (.90, rather than the conventional .80), and we started by entering the following assumptions:

Days of study: 56 [eight weeks of “push” intervention].

Number of decision time points per day: 4.

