Another factor in our decision to include pregnant women is that, had we decided to exclude them, the regulations in 45 CFR 46.204 require that we justify the exclusion. In reviewing recent literature on the bioethics of research in pregnant women, we found a strong trend toward advocacy for a default of inclusion rather than exclusion, for reasons of social justice (Goldkind et al., 2010; Macklin, 2010; Blehar et al., 2013; White, 2015; Hunt et al., 2017). In other words, bioethicists seem to be moving toward a consensus that exclusion of pregnant women from research should carry a heavier burden of proof than inclusion. We do not think we can meet that burden of proof for this protocol.

4. Evaluation of risks/discomforts and benefits ratio

The formative-interview phase of this study is minimal risk; the clinical-trial phase is more than minimal risk.

Potential benefits

Direct Benefits

The formative-interview phase is not expected to provide any direct benefit.

The clinical-trial phase may provide a direct benefit for participation who are randomized to the JITAI group. For OBOT participants (in both the JITAI and EMA groups), the buprenorphine administered during the study will probably decrease illicit opioid use, and the weekly counseling may further reduce opioid and other drug use and reduce HIV-risk behaviors.

Indirect Benefits

This study is likely to yield generalizable knowledge about mobile interventions for addiction.

Risks

Risks associated with interviews in the formative phase

The in-depth part of the interview will include questions about day-to-day challenges. This part of the interview will be conducted only by investigators who have the clinical background required to respond swiftly and sensitively to any unexpected reactions. One of those investigators, for example, has safely overseen more than 80 research sessions in which participants were administered moderate or high doses of the psychedelic drug psilocybin, a situation that calls for highly tuned clinical skills. The other investigator has a doctorate in social work, with extensive practicum experience in recovery centers. Our clinic's master-level counselor will also be standing by.

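### H1, a primary proximal test, uses random intercepts and autoregressive errors with no by-person message slope or clustered standard error; if response to messages varies between people, its standard error is too small

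*Combined protocol and SAP*

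**What the plan says.** The Précis lists as primary outcome 1: "Proximal effects of CBT and ACT messages in the JITAI group: decreases over 20-minute intervals in craving and negative mood" (with increases in self-efficacy). Section I.2, Hypothesis 1, gives the model: "We will use multilevel random-intercept models (with data from the JITAI group only) to test the hypothesis of a proximal benefit of messages". The post rating is the dependent variable, the pre rating is a covariate, and the main predictor is active message (CBT or ACT) versus none. On dependence it says: "We will use an autoregressive error structure to account for within-person correlations". It names no by-person slope for message type and no robust or clustered standard error.

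Hypothesis 2 (primary outcome 2, strategy-situation fit) and Hypothesis 5 use models described as similar to those for H1. Only Hypothesis/analysis 6 names slopes: "we will use multilevel models with person-specific slopes to quantify the relative overall effectiveness of CBT vs. ACT messages".

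The plan looks beyond the enrolled participants. Section L.4 says "This study is likely to yield generalizable knowledge about mobile interventions for addiction", and section E.3 says that recruiting both treatment streams "may expand the population to which we can generalize our results". It also treats variation in response as an open question. The Précis aims to "clarify when and for whom the generic components of such apps are effective or not", and section E.3 says "we will test whether the interviewed participants respond differently from newly enrolled participants".

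**The concern.** A random intercept absorbs stable differences in level between people. An autoregressive error absorbs correlation that fades with time. Neither absorbs a stable difference in how much a person responds to messages, because the covariance from such a difference does not decay with lag. If such differences exist, the model treats each person's many moments as more informative about the average effect than they are.

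At stake is the precision of a primary result. Section J itself says there is little precedent for the size of a proximal effect, so the estimate and its uncertainty matter as much as the significance verdict. Section I.2 also counts a significant benefit on any one outcome as partial support, which leaves the p-value exposed if the true mean is smaller than planned.

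**Working it through.** **The plan's own figure.** Section J says 25 evaluable JITAI participants suffice for H1. Inputs: 56 days, 4 decision points a day, randomization probability 0.67, availability starting at 0.80 and averaging 0.60, effect starting at 0.05 and averaging 0.15, power 0.90. I used an F test on a quadratic effect with 3 and N − 6 df. The noncentrality is N times the sum over decision points of availability × .67 × .33 × effect². This gives 24 to 26 across reasonable readings of the curves. It gives exactly 25 (power .905) with the effect peaking at day 28 and availability falling to the last day. The figure reproduces and is not in dispute.

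**H1 inputs.** Moments per person: 56 × 4 × .60 = 134.4, of which two-thirds (89.6) are active and one-third (44.8) control. N = 50 (section J). Tau is assumed.

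**H1 formulas.** In residual-SD units, the within-person variance of one person's contrast is
v = 1/89.6 + 1/44.8 = .0335.
The planned model reports SE = √(v/50) = .026 whatever tau is. The true SE is √((v + tau²)/50). Hence:
- ratio = √((v + tau²)/v)
- type I error at zero mean = 2 × (1 − Φ(1.96/ratio))
- coverage = 1 − that value, whatever the true mean
- half-width = 1.96 × SE

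| tau (assumed) | true/reported SE | coverage | type I error, zero mean | correct half-width (reported: .051) |
|---|---|---|---|---|
| 0 | 1.00 | .95 | .05 | .051 |
| .05 | 1.04 | .94 | .059 | .053 |
| .10 | 1.14 | .91 | .085 | .058 |
| .20 | 1.48 | .81 | .19 | .075 |
| .30 | 1.92 | .69 | .31 | .097 |

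N cancels from the ratio, so enrolling more people does not cure it. The number of moments matters little: at tau .10, type I error is .081 with 117.6 moments (the seven pure-push weeks) and .098 with 184 (82% completion).

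**Plausible tau.** At mean .15, the share of people with a negative effect is Φ(−.15/tau): 0.1%, 7%, 23% and 31% at tau .05, .10, .20 and .30. So .10 is a middle case and .20 and .30 are high. Pooling CBT with ACT shrinks tau. If each effect has SD s across people and they correlate r, the pooled SD is s√((1 + r)/2). With s = .10 and r = 0 this is .071, and type I error is .068.

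**Simulation with autoregressive errors modelled.** With 50 people, 134 moments, REML fitting, the pre rating as covariate and 1,000 runs, type I error under the planned model was .057, .064, .087 and .217 at tau 0, .05, .10 and .20. With person-clustered SEs (t, 49 df) it was .059, .047, .049 and .045.

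**H2.** The 89.6 active moments fall into four cells (CBT or ACT, controllable or not) of 22.4 each at a 50-50 split. The interaction variance per person is 4/22.4 = .179.
- *By-person Type slope with SD tau.* If person i's share of controllable moments is p_i, with mean .5 and SD s_p, the estimate picks up (2/N)Σb_i(2p_i − 1), which adds 16·tau²·s_p² per person. This is zero only if every person is at 50-50. With tau = .20 and s_p = .25 or .35 (assumed) it adds .040 or .078. The ratios are √(.219/.179) = 1.11 and √(.257/.179) = 1.20, and type I error is about .08 and .10.
- *By-person interaction slope with SD .30 (assumed).* It adds .09 even under perfect balance. The ratio is √(.269/.179) = 1.23, and type I error is about .11.

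Simulations of these three H2 cases with independent errors gave .075 to .08, .10 to .12, and .11 to .12, against about .06 with clustered SEs.

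**The case against.** The strongest reply is that the harm depends on a quantity no one knows. The remarks about for whom components work, and about interviewed participants, are questions to be examined and do not forecast a spread. H6 concerns CBT versus ACT, not active versus none. That stands, so the point is conditional.

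Second, the middle case is modest. At tau .10 an interval around .15 moves from about .099–.201 to .092–.208, and power with the correct SE is .999. That also stands.

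Third, section I plans p-values, support rules and Bayes factors but names no confidence interval for H1. This does not rescue the model, because the same SE drives the p-value.

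Fourth, the generalization remarks sit in the benefits and recruitment text and do not define the H1 estimand. They are indirect evidence. If inference were meant only for the enrolled participants, the planned SE would suit it, but the plan nowhere says so.

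A reader might infer that H1 has an inflated false-positive rate as designed. The documents do not support that. Inflation above .05 needs a mean of zero with some people helped and others made worse. If no message affects anyone, tau is zero and the test is valid. Nor should a reader infer that the sample size is wrong, since the 25 reproduces and the 50 is set by H2. Nor does the plan ignore person-level slopes throughout, since H6 has them.

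**Conclusion.** The point holds in conditional form and should be fixed. H1 is positively specified with a random part and an error structure that in effect set between-person variation in message effect to zero, without justification. The understatement is negligible at tau of .05 or less, moderate at .10 (SE 14% too small relative to the reported value, coverage .91) and large at .20 (coverage .81). All of this rests on assumed values of tau, on 134.4 moments per person, and on the average effect beyond the enrolled people being the target. At d = .15 the significance verdict for H1 would usually survive; what suffers is the stated precision.

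H2 shares the exposure, because a 50-50 split overall (section J) does not imply balance within each person and a by-person interaction slope does not cancel at all. The H2 sizes rest on further assumptions about how controllability varies between people. H5 uses the same model family with its random effects unstated, which is under-specification rather than a wrong model.

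**What to change.** In H1, add a by-person random slope for active versus control, with Satterthwaite or Kenward-Roger degrees of freedom. Alternatively, or if that model does not converge, use person-clustered SEs with a small-sample correction (CR2-type). In H2, use the same clustered SEs, or by-person slopes for Intervention Type and for its interaction with controllability. State the random effects for H5. Leave H6 as it is.

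The cost is one or two sentences in section I.2, with no change to the enrollment target. At tau = 0 almost nothing is lost: the H1 half-width goes from .051 to .052 (t on 49 df). Where heterogeneity is real, intervals widen. H1 power at d = .15 with N = 50 is about .999, .97 and .84 at tau .10, .20 and .30, the last below the desired .90.

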For participants in the JITAI group, the content will be as follows:

1. “Pre” Assessment

—“Are you available now?” (If not, allow postponement up to 60 minutes.)

Baseline assessment of mindfulness with 2 items from the CAMS-R (Feldman et al., 2007) as adapted for EMA by Moore and colleagues (2016).

—“I am able to focus on the present moment.” (VAS slider 0-100)

—“I am able to accept the thoughts and feelings I have.” (VAS slider 0-100)

Baseline assessment of negative mood with items from the PROMIS questionnaire (Bjorner et al., 2014) as adapted for EMA by Moore and colleagues (2016).

—“I feel depressed.” (VAS slider 0-100)

—“I feel anxious.” (VAS slider 0-100)

—“I feel angry.” (VAS slider 0-100)

—“I feel stressed.” (VAS slider 0-100)

Baseline assessment of boredom, cue exposure, and drug craving:

—“I feel bored.” (VAS slider 0-100)

—“People, places, or things’ are reminding me of drugs.” (VAS slider 0-100)

—“I am craving drugs.” (VAS slider 0-100; also indicate which drugs)

Baseline assessment of situation category:

—“The best description of my situation right now is...

at home

at work

out doing obligations

out socializing or enjoying myself

other”

Baseline assessment of place:

— The place where I am is pleasant and comfortable (not too hot/cold, noisy, ugly, dangerous, etc.). (VAS slider 0-100)

— “I have privacy right now (or could easily get privacy if I wanted).” (VAS slider 0-100)

— “I could easily be somewhere else right now if I wanted.” (VAS slider 0-100)

Baseline assessment of activity:

— “What I’m doing right now is enjoyable for me.” (VAS slider 0-100)

— “What I’m doing right now is important to me.” (VAS slider 0-100)

— “I could easily get out of what I’m doing right now.” (VAS slider 0-100)

Baseline assessment of general self-efficacy:

—“I feel in control of my *responses* to what’s happening right now.” (VAS slider 0-100)

Baseline assessment of recovery self-efficacy, using an item adapted from Kranzler et al. (2016):

—“I’m confident that I can stick to my treatment goals for the rest of today/tonight.” (VAS slider 0-100)

Use of drugs since the previous assessment:

- “I have used an opiate since the previous assessment.” (yes/no)
- “I have used cocaine since the previous assessment.” (yes/no)
- “I have used other drugs since the previous assessment.” (yes/no)

Note: This “pre” assessment will also be given to the EMA-only group four times a day. Everything that follows will be given only to the JITAI group.

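### Partial support for Hypotheses 1 and 2 needs only one of several unadjusted tests, so it can arise falsely about two to four times as often as the 2.5% per-test rate, depending on how correlated the outcomes are

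*Combined protocol and SAP*

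**What the plan says.** Section I.2 fits a separate multilevel model for each outcome. For Hypothesis 1 the decision rule is: "A significant beneficial effect on any of the outcome measures (self-efficacy, craving, mood, message helpfulness) will be taken as partial support for the hypothesis". For Hypothesis 2 the trigger is: "A significant interaction (in the expected direction) on any of the outcome measures", over the same four outcomes. Both hypotheses also have a stronger grade: "significant beneficial effects on all the outcome measures will be taken as full support".

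Section I.3 states: "The criterion for statistical significance will be set at $p \leq 0.05$, two-tailed". It gives no multiplicity adjustment, no order of testing and no lead outcome. Bayes factors are reserved for hypothesized effects that miss significance.

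Two details of Section E.3 fix the number of tests:

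- The usefulness rating is part of the 'post' assessment only when a CBT or ACT message was given. It is not collected after the control message, and it has no 'pre' value.
- Mood is introduced as "Baseline assessment of negative mood with items from the PROMIS questionnaire" and consists of four sliders (depressed, anxious, angry, stressed). Self-efficacy has two sliders, one general and one about recovery. The plan defines no combined score for either.

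The Précis lists the proximal effects on craving, negative mood and self-efficacy, and strategy-situation fit, among the primary outcome measures.

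**The concern.** When one success among several is enough to claim support, the chance of a false claim exceeds the chance for any single test. Both proximal primary hypotheses use such a rule, with every test at the unadjusted level. A report of partial support would therefore carry more error than the criterion in Section I.3 suggests.

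The matter is sharper for Hypothesis 1. Helpfulness cannot be compared between active and control messages, so the requirement that all four outcomes be significant cannot be met. Partial support is then the only positive verdict Hypothesis 1 can return, and it is the verdict with the raised error rate.

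Without a defined mood score or self-efficacy measure, the number of tests behind the rule also remains open until analysis.

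**Working it through.** **Inputs.** Two-tailed alpha of .05 (Section I.3). The rules also require the beneficial or expected direction (Section I.2), so the rate of false support per test is .05/2 = .025. Outcomes: three for Hypothesis 1 (self-efficacy, craving, mood) and four for Hypothesis 2, which compares CBT with ACT and so has helpfulness in both conditions. Item by item: 4 mood + 2 self-efficacy + 1 craving = 7 for Hypothesis 1, and 8 with helpfulness for Hypothesis 2.

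**The plan's own figure.** Section J gives 25 evaluable participants for Hypothesis 1. A noncentral-F calculation for a microrandomized trial returns 25 when the effect peaks at day 28 or 29, and 24 at day 27. It uses the Section J inputs (56 days, 4 points a day, probability .67, availability .80 falling to a mean of .60, d = .05 rising to a mean of .15, power .90) and assumes the calculator's defaults. The 49 for Hypothesis 2 cannot be rebuilt, because the reduced availability input is not stated. The documents give no error rate for the any-of rule.

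**Independent outcomes.** P(false partial support) = 1 − (1 − .025)^k.

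- k = 3: 1 − .975³ = .0731, or 2.9 times .025.
- k = 4: 1 − .975⁴ = .0963, or 3.9 times.
- k = 7: 1 − .975⁷ = .1624, or 6.5 times.
- k = 8: 1 − .975⁸ = .1833, or 7.3 times.

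**Correlated outcomes.** With equal correlation r between the test statistics, each signed so that positive means benefit, and c = 1.96:

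P = 1 − ∫ φ(u) · Φ[(c − √r·u)/√(1 − r)]^k du.

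The values of r are assumptions.

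| r | H1, k = 3 | H2, k = 4 | H1 by item, k = 7 | H2 by item, k = 8 |
|---|---|---|---|---|
| 0 | 7.3% (2.9×) | 9.6% (3.9×) | 16.2% (6.5×) | 18.3% (7.3×) |
| .3 | 6.8% (2.7×) | 8.7% (3.5×) | 13.7% (5.5×) | 15.2% (6.1×) |
| .5 | 6.3% (2.5×) | 7.8% (3.1×) | 11.5% (4.6×) | 12.5% (5.0×) |
| .7 | 5.5% (2.2×) | 6.5% (2.6×) | 8.9% (3.6×) | 9.5% (3.8×) |
| .9 | 4.2% (1.7×) | 4.7% (1.9×) | 5.7% (2.3×) | 6.0% (2.4×) |

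**After adjustment.** Holm's first step tests the smallest p-value at .05/k. With independent outcomes, the rate in the favourable direction becomes 1 − (1 − .05/6)³ = .0248 for three outcomes and 1 − (1 − .05/8)⁴ = .0248 for four.

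**Power after adjustment.**

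- Hypothesis 1, first step at .05/3 = .0167: the N for power .90 rises from 25 to 31. Power at the planned 50 is .997.
- Hypothesis 2, first step at .05/4 = .0125 (normal approximation): the plan's power of .90 implies a noncentrality of 1.960 + 1.2816 = 3.2415. Power becomes Φ(3.2415 − 2.498) = .77. The d detectable with power .90 becomes .16 × (2.498 + 1.2816)/3.2415 = .16 × 1.166 = .187. Keeping d = .16 at power .90 would need 49 × 1.166² ≈ 67 participants.
- For the 70-30 controllability split in Section J: .174 × 1.166 = .203.

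**The case against.** The plan grades its conclusions in advance and requires the right direction. Full support needs every outcome, which is a conservative rule. That stands: nothing here affects full support for Hypothesis 2. It does not protect Hypothesis 1, where full support is out of reach as written.

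The outcomes are rated by one person in one short sequence, so positive correlation is likely and the independence figures are close to a ceiling. That also stands. A reader might infer that false support is three to four times the per-test rate as a matter of fact. The documents give no correlations, and those multiples require independence. The excess shrinks with correlation but does not vanish: 1.7 and 1.9 times remain at r = .9.

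Item-by-item testing is only a possibility, since Section I.2 names mood and self-efficacy as one outcome each. The seven- and eight-test figures are therefore conditional. A reader might apply eight tests to both hypotheses, but for Hypothesis 1 the maximum is seven.

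The plan does show restraint elsewhere. Section I.2 promises to say that the additional strategy-situation analyses had no prior hypotheses, and to label the exploratory trait analyses and state their number. Neither promise reaches the any-of rule.

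A reader might also compound the error over all primary outcomes, including the distal ones ("group differences in distal effects of treatment (week 11 versus week 2) in terms of self-efficacy and coping flexibility"). The plan makes no any-of claim across hypotheses, and Hypothesis 3 has no such rule, so a pooled rate would describe a claim nobody makes.

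The strongest objection is cost. Hypothesis 2 set the sample size, with 49 needed and 50 planned, so adjustment there takes real power.

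**Conclusion.** The concern holds for the partial-support label in Hypotheses 1 and 2. Against 2.5% per test, the rate of false partial support is at most 7.3% for Hypothesis 1 and 9.6% for Hypothesis 2 when outcomes are independent or positively correlated. Over assumed correlations of .7 to .3 it is about 5.5–6.8% (2.2–2.7 times) and 6.5–8.7% (2.6–3.5 times). If the sliders were tested singly, it would be 11.5–16.2% and 12.5–18.3% at r = .5 to 0.

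These figures assume equal correlation between outcomes and no true effect on any of them. Separately, and without any assumption about correlation, Hypothesis 1 cannot reach full support as written. The plan should be changed before analysis; the point does not call the design or the microrandomization into question.

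**What to change.** Amend Section I.2 before analysis:

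1. Remove message helpfulness from the Hypothesis 1 outcomes, leaving self-efficacy, craving and mood. This matches the proximal outcomes in the Précis and makes full support attainable. Keep helpfulness for Hypothesis 2, noting that its model has no 'pre' covariate.
2. Define one mood score, for example the mean of the four sliders, and one self-efficacy measure. Section E.3 labels the two self-efficacy items separately, so either their mean or one item named in advance would serve.
3. Base partial support on Holm-adjusted p-values across the three Hypothesis 1 outcomes and, separately, across the four Hypothesis 2 outcomes. Keep the direction requirement.
4. Leave the all-outcomes rule for full support unadjusted.

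The change is one of wording, but its cost in power is uneven. Hypothesis 1 loses almost nothing: first-step power at 50 participants stays at .997 under the plan's assumptions. For Hypothesis 2, first-step power for a single outcome at d = .16 falls from .90 to about .77, and the d detectable with power .90 rises to about .187. That is still below the .21 to .39 that Section J cites from an earlier study, as is .203 under a 70-30 split. Section J should restate the Hypothesis 2 power on this basis. Defining the scores also limits the loss: with eight separate tests, first-step power would be about .69.
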